For rare instances or emergency cases, the *Pharmacy Guidelines and Instructions for DAIDS Clinical Trials Networks* permits shipment by mail or courier of study product from the site directly to participants. This method should only be used on a short-term basis and if permissible by the site's institution. If this method is to be implemented, each site's Pharmacist of Record (PoR) must develop appropriate procedures for the shipment or courier of study product to identified participants in accordance with these guidelines, and document chain of custody. Prior to implementation, the site PoR must coordinate with site clinic staff to determine the appropriateness of this method for applicable protocols and participants.

4. In section 6.1, Schedule of Evaluations, the visit window for weeks 36 to 96 has been changed as shown below:

Evaluation	Screening	Pre-Entry	Entry	Post-Entry Evaluations (Weeks)									Confirmation of VF	Premature Study/Treatment Discontinuation
				2	4	12	24	36	48	60	72	84		
Visit Windows				± 1 wk	± 2 wks			- 4 wks, + 8	12 wks					

5. In section 6.2.3, Post-Entry Evaluations, the following instructions have been added to the On-Treatment Evaluations subsection:

Alternate Completion of Post-Entry Evaluations

- **If the participant's visit is postponed within the extended visit window, the site should ensure that the participant has sufficient supply of the study products to last him or her to the point when he or she can come to the clinic.**
- **If the participant does not have enough supply of study products to allow the visit to be postponed, the site must attempt to contact the participant by phone or other method available.**
 - During the remote contact for visit week 72 or week 96, the site should conduct a safety follow-up (such as inquiring about signs and symptoms) to determine if any AEs or serious adverse events (SAEs) have occurred since the last visit and if the participant needs medical follow-up. Additionally, the site should complete the questionnaires and adherence assessment per section 6.3.9, section 6.3.10, and MOPS section 4. All other evaluations and stored samples that will be missing for the visits, and the reason why they are missing, must be documented in the participant's study file.
 - At all visits except week 96, the site should confirm if the participant is able to

receive a new supply of study medications if it is shipped via mail or sent via courier (see section 5.1.2). If a participant is unable to pick up or receive study medications via shipment or courier, the site should consult the study core team ([contact]) for further guidance.

- If safety laboratory evaluations, and a pregnancy test for female participants of reproductive potential, cannot be performed, the continuation of study treatment is at the discretion of the Investigator of Record (IoR). The site should inform the study core team of the decision of the IoR.

6. In section 6.2.4, Discontinuation Evaluations, the following instructions have been added to the Premature Treatment Discontinuation Evaluations subsection:

Alternate Completion of Post-Entry Evaluations

- The visit can be postponed within the extended visit window if needed to safely conduct a face-to-face clinic visit. If the participant can safely be seen in the clinic, the site should perform all the evaluations for the visit per the SOE in section 6.1, Letter of Amendment (LOA) #1, and LOA #2.
- If the visit cannot be completed with a face-to-face visit despite the extended visit window, the site must attempt to contact the participant by phone or other method available. During the remote contact for visit week 72 or week 96, the site should conduct a safety follow-up (such as inquiring about signs and symptoms) to determine if any AEs or SAEs have occurred since the last visit and the participant needs medical follow-up. Additionally, the site should complete the questionnaires and adherence assessment per section 6.3.9, section 6.3.10, and MOPS section 4. All other evaluations and stored samples that will be missing for the visits, and the reason why they are missing, must be documented in the participant's study file.

7. In Appendix I, Sample Informed Consent (SIC), the following has been added as a new subsection, before the Optional Lumbar Puncture subsection, in the section WHAT DO I HAVE TO DO IF I AM IN THIS STUDY?:

COVID-19 Pandemic Considerations

During the ongoing COVID-19 pandemic, the following adjustments may be made to your study visits:

- If there is an outbreak of COVID-19 in your community and you are unable to come to the study clinic, your study doctor or staff member will try to contact you by phone or other remote method if you have a study visit due. During this contact:
 - You will be asked about your health since your last study visit or contact.

1.1 Purpose

This Primary Statistical Analysis Plan (SAP) describes the primary and secondary outcome measures and additional outcome measures of the A5324 study that will be included in the primary manuscript, and which address, at a minimum, the major primary and secondary objectives of the study. The Primary SAP outlines the general statistical approaches that will be used in the analysis of the study. It has been developed to facilitate discussion of the statistical analysis components among the study team, and to provide agreement between the study team and statisticians regarding the statistical analyses to be performed and presented in the Primary Analysis Report. It also describes the results for the primary and secondary outcome measures that will be posted on ClinicalTrials.gov.

Detailed outlines of tables, figures, and coding descriptions that will be included in the Primary Analysis Report are included in the Analysis Implementation Plan (AIP).

Analyses for the Primary Analysis Report will be finalized once the last participant has completed the week 96 study visit, all queries have been resolved, and the study database closure/data lock has been completed.

Outlines of analyses for other objectives and outcome measures not included in the Primary SAP will be provided in a separate SAP.

1.2 Version History

Major changes to the previous version are noted in **bold face** throughout the document.

The SAP has been updated prior to final analysis and based on discussions with the study team.

Version	Changes Made	Date Finalized
1	Original Version	05/19/2017
2	Update for Protocol v2.0, LOA #3	03/28/2019
3	Updated for final analysis and LOA #4: Updated the viremia outcome to exploratory, added a BDI-related exploratory outcome, updated the functional status analysis, added missing data handling, and added appendices describing neurocognitive test scoring procedures and IADL scoring procedures; clarifications throughout	02/12/2021

2 Study Overview

2.1 Study Design

This is a phase IV randomized, double-blinded, placebo-controlled study to assess the efficacy of adding Maraviroc (MVC) and Dolutegravir (DTG) to the current antiretroviral therapy (ART) of HIV-infected individuals with undetectable (<50 copies/mL) plasma HIV-1 RNA, who have mild to moderate neurocognitive impairment, with a primary outcome of improvement in neurocognitive performance.

DURATION 96 weeks

SAMPLE SIZE 186 participants

POPULATION Participants will have HIV-associated neurocognitive disorder (HAND) as defined by the Frascati criteria, plasma HIV-1 RNA <50 copies/mL within 90 days prior to entry, and no more than one plasma HIV-1 RNA ≥ 50 and <200 copies/mL in the past 6 months prior to entry with a subsequent plasma HIV-1 RNA <50 copies/mL, and on stable ART for at least 6 months prior to entry with no plans to change treatment.

STRATIFICATION Participants will be randomized in a stratified manner. Stratification variables will be CD4+ nadir (≤ 100 vs. > 100 cells/mm³), and HAND severity (asymptomatic neurocognitive impairment [ANI] vs. mild neurocognitive disorder [MND] / HIV-associated dementia [HAD]).

REGIMEN At entry participants will be randomized to one of the following:
- Arm A: Add to their existing ART: placebo for MVC and placebo for DTG
- Arm B: Add to their existing ART: DTG and placebo for MVC
- Arm C: Add to their existing ART: MVC and DTG

2.2 Hypotheses

2.2.1 Primary

In HIV-1-infected participants with suppressed plasma viremia and at least mild neurocognitive impairment, improved neurocognition and increased functional capacity over 48 weeks will be seen with addition of Maraviroc (MVC) plus Dolutegravir (DTG) (Arm C) compared to DTG only (Arm B) and compared to placebos (Arm A). Addition of DTG only (Arm B) compared to placebos (Arm A) will result in improved neurocognition over 48 weeks and increased functional capacity.

2.2.2 Secondary

Changes in peripheral blood and cerebrospinal fluid (CSF) biomarkers will parallel improvement in neurocognitive performance following addition of DTG alone or MVC and DTG.

2.3 Study Objectives

Analysis of the study objectives below will be analyzed under a superiority framework, to conduct pairwise comparisons of the three arms.

2.3.1 Primary

1. To determine whether intensification with MVC and DTG (Arm C) will improve neurocognitive functioning at week 48 in participants who have at least mild neurocognitive impairment, are on a stable antiretroviral therapy (ART) regimen, and have plasma HIV-1 RNA <50 copies/mL, over DTG plus placebo for MVC (Arm B) and over placebo of both drugs (Arm A).
2. To determine whether DTG with placebo for MVC (Arm B) will improve neurocognitive functioning at week 48 over placebo of both drugs (Arm A).

2.3.2 Secondary

1. To determine the safety and tolerability of MVC and DTG when added to a stable ART regimen. The safety and tolerability measures will include time to discontinuation of any study medication due to adverse events (AEs), proportion of Grade 3 or Grade 4 clinical AEs, proportion of Grade 3 or Grade 4 laboratory abnormalities, and summaries of all treatment related AEs.
2. To determine whether intensification with MVC and DTG will improve neurocognitive functioning at weeks 24, 72, and 96.
3. To determine whether functional status improves at week 48 after intensification with MVC and DTG (Arm C) to a greater extent than when intensified with DTG and placebo for MVC (Arm B) or placebo of both drugs (Arm A).
4. To assess the effect of adding MVC and DTG on biomarkers in peripheral blood and CSF.
5. To assess the association between **plasma** and CSF biomarkers, neuropsychological performance, and DTG and MVC pharmacokinetics (PK) throughout the course of the study.
6. To assess whether the addition of DTG alone (Arm B) or DTG and MVC (Arm C) is associated with maintenance of plasma HIV-1 RNA <50 copies/mL.
7. To assess changes in blood CD4+/CD8+ counts after intensification with DTG and MVC (Arm C), DTG alone (Arm B) or placebos (Arm A).
8. To determine associations between peripheral blood immunologic markers (s100 β , soluble CD14) and changes in neurocognitive function at week 48.
9. To determine the relationship between changes in CCR5 ligand levels (MIP-1b) and inflammatory marker changes in both peripheral blood and CSF.
10. To determine the effect of DTG intensification on residual viremia, cellular HIV-1 RNA expression, total cellular HIV-1 DNA, and 2 long terminal repeat sequences (LTR) DNA, and to determine whether these virologic changes are associated with week 48 neurocognitive function.

2.4 Overview of Sample Size Considerations

Based on previous studies, a standard deviation (SD) of 0.7 in the 48-week change in normalized neurocognitive test score is assumed. In the sample size calculation, the null hypothesis is that there is no difference in changes of neurocognitive functioning from baseline to week 48 across the treatment arms, while the alternative hypothesis is that the change of neurocognitive functioning is at least 0.5 higher for the (MVC and DTG) arm. A Bonferroni correction has been applied to account for multiple comparisons between treatments. One interim analysis of efficacy

is planned in the middle of the study and the adjusted sample sizes assume a 15% loss to follow-up. To achieve a power of 90%, we would expect a sample size of 62 participants per group for a total 186 participants on study. See Protocol section 9.4 for further details.

2.5 Overview of Formal Interim Monitoring

Routine SMC reviews by the Neuro SMC assess the study progress via reviewing accrual, study status, screening failures, and toxicity at least annually. In the middle of the study, when 50% of participants are enrolled and followed for 48 weeks, an efficacy interim review will occur. This review will consist of a review of the assumed standard deviation (SD=0.7) and pairwise comparisons between the three blinded treatment arms. The pairwise comparisons will be made using repeated confidence intervals and Bonferroni correction, and will use a threshold p-value of 0.0007 for each comparison to assess significance. See Protocol section 9.5 for details.

3 Outcome Measures

3.1 Primary Outcome Measures

1. The change in normalized composite neurocognitive test score at week 48 from pre-entry. This test score is further defined below.
 - Aligns with Primary Objectives 1 & 2

The normalized neurocognitive test score for domestic participants is defined as the average of z-scores on the following tests:

- Stroop color naming [English: NE7041, Spanish: NE7101]
- Stroop word reading [English: NE7041, Spanish: NE7101]
- Stroop interference trial [English: NE7041, Spanish: NE7101]
- Grooved pegboard dominant [NE7046]
- Grooved pegboard non-dominant [NE7046]
- HVLTR Learning trials [NE7097]
- HVLTR Delayed recall [NE7097]
- HVLTR Delayed recognition [NE7097]
- Semantic verbal fluency [NE7098]
- Letter fluency [NE7098]
- Trail Making A [NE7099]
- Trail Making B [NE7099]
- WAIS-III Symbol search [NE7101]
- Digit Symbol [NLW0016]

The WRAT-4 word reading total [English: NLW0018] (WAT Spanish Word List word reading total [Spanish: NLW0020]) was also administered at domestic sites but will not be included in the average z-score calculation and instead will be analyzed separately.

The normalized neurocognitive test score for international participants is defined as the average of z-scores on the following tests:

- Grooved pegboard dominant [NE7046]
- Grooved pegboard non-dominant [NE7046]
- HVLTR Learning trials [NE7097]

- HVLT-R Delayed recall [NE7097]
- HVLT-R Delayed recognition [NE7097]
- Semantic verbal fluency [NE7098]
- Digit Symbol [NLW0016]
- Timed Gait [NE7090]
- Finger Tapping Dominant [NE7095]
- Finger Tapping Non-dominant [NE7095]
- Color Trail 1 [NE7096]
- Color Trail 2 [NE7096]

The International HIV Dementia Scale (IHDS) [NE7061] was also administered at international sites but will not be included in the average z-score calculation and instead will be analyzed separately.

For time point assessment of impairment (baseline, weeks 24, 48, 72, 96), z-scores will be calculated by subtracting a demographically appropriate (adjusted for age, race, sex, and years of education) norm and dividing by a demographically appropriate standard deviation. Z-score calculations are described in detail in Section 0. The z-scores will be calculated using the raw scores from the neurocognitive tests.

Assessment of change over time in neurocognitive impairment will be calculated by subtracting the average z-scores of the two time points of interest.

The individual scores are separated into six component domains (**plus the two separate tests WRAT and IHDS mentioned above**). The z-score for each domain is the average of standardized individual NP z-scores listed under each domain:

- Fine motor Skills/Complex Perceptual
 - Grooved pegboard dominant – both domestic and international
 - Grooved pegboard non-dominant – both domestic and international
 - Finger Tapping dominant – international
 - Finger Tapping non-dominant – international
 - Timed Gait - international
- Speed of Information Processing
 - Digit Symbol – both domestic and international
 - Stroop color naming – domestic
 - Stroop word reading – domestic
- Executive Function
 - Trail Making B – domestic
 - Stroop interference trial – domestic
 - Letter Fluency – both domestic and international
 - Semantic Verbal Fluency – both domestic and international
 - Color Trails 2 – international
- Verbal Learning
 - HVLT-R Learning Trial – both domestic and international
- Verbal Memory
 - HVLT-R Delayed recall – both domestic and international

- HVLIT-R Delayed recognition – both domestic and international
- Attention/Working Memory
 - Trail Making A – domestic
 - WAIS-III symbol search – domestic
 - Color Trails 1 – international
- IHDS – international
- Premorbid Skills
 - WRAT-4 Reading / WAT Spanish Word List – domestic

Based on the z-scores, domain deficit scores (DDS) will be computed for the domains, and the global deficit score (GDS) will be computed using the total battery. The GDS emphasizes impairment, reduces minimal learning/practice and has the advantage of reducing ‘sum to zero’ effects seen with counterbalancing positive and negative scores in a subject’s assessment. However, this approach does minimize the ability to observe subtle changes as scores are grouped into larger categories.

DDS and GDS are derived from the standardized scores by the following algorithm:

- If z-score is greater than -1.0, then DS is 0;
- If z-score is [-1.5, -1.0] then DS is 1;
- If z-score is [-2.0, -1.5] then DS is 2;
- If z-score is [-2.5, -2.0] then DS is 3;
- If z-score is [-3.0, -2.5] then DS is 4;
- If z-score is smaller than -3.0 then DS is 5;
- If z-score is missing then DS is missing;

The DS categories are defined as:

- 0 – Normal
- 1 – Mild
- 2 – Mild to Moderate
- 3 – Moderate
- 4 – Moderate to Severe
- 5 – Severe

3.2 Secondary Outcome Measures

1. Treatment related adverse events
 - Aligns with Secondary Objective 1
 - **Time to discontinuation of any study medication due to adverse events**
 - **Proportion of Grade 3 or Grade 4 clinical AEs**
 - **Proportion of Grade 3 or Grade 4 laboratory abnormalities**
 - **Summaries of all AEs where the site indicated some relationship to study treatment.**
2. Change from baseline of normalized composite neurocognitive test score at weeks 24, 72, and 96. Change from baseline of normalized component neurocognitive test scores at weeks 24, 48, 72, and 96 will also be examined.
 - Aligns with Secondary Objective 2
 - See primary outcome for details on composite neurocognitive test scores
 - Component neurocognitive test scores consist of domain scores

- Change from baseline in the domain deficit scores and GDS to weeks 24, 48, 72, 96
3. Change from baseline in functional status scores based on the IADLs form at weeks 24, 48, 72, and 96.
 - Aligns with Secondary Objective 3
 - **Functional change is defined as a change from baseline in IADL score. The IADL scoring is defined in Section 7.**
 4. Change from baseline of peripheral blood and CSF biomarkers at week 48.
 - Aligns with Secondary Objective 4
 - Potential list of biomarkers includes:
 - i. Blood: sCD14, MIP-1 β , TNFr-II, VCAM-1, NFL
 - ii. CSF: MIP-1 β , NFL, neopterin, IP-10
 5. Plasma HIV-1 RNA \geq 50 copies/mL at weeks 24, 48, and 96.
 - Aligns with Secondary Objective 6
 6. CD4+ T-cell counts and changes from baseline to weeks 24, 48, and 96.
 - Aligns with Secondary Objective 7
 7. CD8+ T-cell counts and changes from baseline to weeks 24, 48, and 96.
 - Aligns with Secondary Objective 7

3.3 Other Outcome Measures

1. Changes from baseline to week 48: residual viremia, cell-associated HIV-1 RNA/DNA/2-LTR circles and SCA, T-cell and monocyte activation.
 - Aligns with Secondary Objective 10
 - Looking specifically at the comparison between DTG only arm and placebo arm to determine the effect of DTG intensification on these factors
 - **NOTE: This outcome measure was listed as secondary in the protocol but the intention was as an exploratory outcome due to lack of funding for testing, specifically for T-cell and monocyte activation**
2. Beck Depression Inventory (BDI) evaluations
 - **New outcome measure**
 - **Change in BDI score (evaluated as the sum of the 21 items) from baseline to weeks 24, 48, 72, and 96**
 - **Change from baseline in BDI score by subscales:**
 - Cognitive (items 1, 2, 3, 5, 6, 7, 8, 9, and 14)
 - Affective (items 4, 10, 12, and 13)
 - Somatic (items 11, 15, 16, 17, 18, 19, 20, and 21)
 - **Percent of participants with a BDI score \leq 13 vs. $>$ 13 at weeks 24, 48, 72, and 96**
3. **Associations of neuropsychological performance with plasma and CSF biomarkers and at weeks 0, 24, 48, 72, and 96 (0 and 48 only for CSF biomarkers); and with DTG and MVC PK at weeks 24 and 48.**
 - **Aligns with Secondary Objectives 5, 8, 9**

4 Statistical Principles

4.1 General Considerations

- The primary analysis and secondary analyses will use the ITT principle (i.e. all randomized participants will be included in the primary analyses).
- The primary analyses will use “as randomized” for group assignment.
- **The missing values for neurocognitive test scores will be imputed at the test level in the following manner:**
 - **When missing values can be attributed to neurologic impairment, the worst 1% score will be imputed for the missing values. Note: If the participant was unable to perform the test due to a disability related to HIV-associated neurological disease (e.g., unable to follow or understand directions, severe impairment in motor controls) this was indicated on the appropriate neuropsychological examination form.**
 - **If the reason for missingness is unknown and observations exist both before and after the missing value, these scores will be averaged and that averaged value will be imputed for the missing value.**
 - **If the reason for missingness is unknown and observations do not exist after the missing value, scores will be imputed by the last observation carried forward method.**
- **Missing data prevalence (of visits and of neurocognitive test scores) will be summarized.**
- **For the neurocognitive test scores, Winsorized estimates may be used for extreme outliers after observing the data.**
- All programs that create permanent study-specific derived datasets or that contribute to analyses of the primary or secondary objectives will be validated according to CBAR SOPs. Primary and key secondary objective results will be verified through independent double programming.
- **Visit and analysis window details:**
 - **Visits occurred at screening, entry, and weeks 2(±1), 4(±1), 12(±2), 24(±2), 48(-4,+8), 72(-4,+8), and 96(-4,+8).**
 - **Analysis windows will be formed around each study visit using the midpoints between adjacent visits as cutoffs and potentially including assessments collected outside the recommended visit windows described in the protocol.**

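### The worst-1% imputation for neurologic inability has no defined reference and no link to the participant's own scores, so a lost test can be scored as improvement

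*SAP*

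**What the plan says.** SAP 4.1 sets the imputation rules for neurocognitive scores: "The missing values for neurocognitive test scores will be imputed at the test level in the following manner". For inability due to neurologic disease, "When missing values can be attributed to neurologic impairment, the worst 1% score will be imputed for the missing values". The reference distribution (norms or trial data), the visits and arms, and the scale (raw or z) are not stated. The participant's own scores are used only when the reason for missingness is unknown. They are then averaged across the gap or carried forward: "If the reason for missingness is unknown and observations do not exist after the missing value, scores will be imputed by the last observation carried".

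The primary outcome in SAP 3.1 is "The change in normalized composite neurocognitive test score at week 48 from pre-entry", and "Assessment of change over time in neurocognitive impairment will be calculated by subtracting the average z-scores of the two time points of interest". The composite is an unweighted mean of 14 test z-scores at domestic sites and 12 at international sites.

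The plan expects very low observed scores. The deficit scale in SAP 3.1 ends with "If z-score is smaller than -3.0 then DS is 5". The SAP Section 6 appendix converts HVLT-R raw scores to z even when they fall below the T-score tables. HIV-associated dementia is included in a randomization stratum (SAP 2.1).

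**The concern.** A fixed low value makes sense when the outcome is the score at one visit. In a change score its effect depends on where the participant started. If the pre-entry z was above the imputed value, inability counts as decline. If it was below, inability counts as gain.

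The rule then also conflicts with the one beside it. Take a participant at -3.5 at pre-entry, with the test missing at week 48 and no other observation. If the reason is unknown, carrying forward gives a change of zero. If the form documents neurologic inability and the norms are the reference, the change is positive, so documented inability scores better than unexplained absence. The error also reaches the deficit-score outcomes in SAP 3.2.

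Because the reference is undefined, two programmers could follow the same sentence and obtain changes of opposite sign for the same participant.

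**Working it through.** **Inputs.** Number of tests m = 14 ("The normalized neurocognitive test score for domestic participants is defined as the average of z-scores on the following tests") or 12 ("The normalized neurocognitive test score for international participants is defined as the average of z-scores on the following tests"), counted from the lists in SAP 3.1. SD of change 0.7, design difference 0.5, power 90%, 15% loss and 62 per group, from SAP 2.4. The baseline z values, the share of participants affected and the trial's test-level mean and SD are not in the documents; the values below are assumptions.

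**The plan's own figure.** SAP 2.4 gives no overall alpha. Assume two-sided 0.05 split over three comparisons (0.0167 each). Then n = 2 × [0.7 × (2.394 + 1.282) / 0.5]² = 52.96 per arm, and 52.96 / 0.85 = 62.3, which agrees with 62. The imputation rule does not enter this calculation. It only supplies the 0.5 yardstick.

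**Formula.** With c the imputed z, b the pre-entry z and k tests lost, the change on one test is c - b. The composite change is k(c - b)/m if the other tests are unchanged.

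**Reading 1: norms.** The 1st percentile of a standard normal is c = -2.326.

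| Pre-entry z | Change on the test | Composite, 1 of 14 | Composite, 1 of 12 |
|---|---|---|---|
| -2.0 | -0.33 | -0.02 | -0.03 |
| -2.5 | +0.17 | +0.01 | +0.01 |
| -3.0 | +0.67 | +0.05 | +0.06 |
| -3.5 | +1.17 | +0.08 | +0.10 |

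The sign is wrong for every baseline below -2.33. On the plan's deficit scale the imputed value is DS 3 (Moderate) and a baseline of -3.5 is DS 5 (Severe), so that test's deficit score also improves by 2.

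**Reading 2: the trial's own scores.** By construction only about 1% of scores on a test lie below c. For illustration, with an assumed test-level mean of -1 to -2 and SD of 1 to 1.25, c lies between -3.33 and -4.91.

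- Baseline -3.0 gives -0.33 to -1.91, always a decline.
- Baseline -3.5 gives +0.17 to -1.41.

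If the value meant the minimum over all visits, reversal could not occur. At domestic sites Grooved Pegboard is capped at 300. If 1% or more of scores sit at that cap, participants at the cap get zero change.

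**Arm mean, reading 1.** If a share p of an arm is affected, the shift is p × k × 1.174 / m at baseline -3.5.

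| p | 2 of 14 tests | 5 of 12 tests |
|---|---|---|
| 2% | 0.003 | 0.010 |
| 5% | 0.008 | 0.024 |
| 10% | 0.017 | 0.049 |

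**The case against.** The text does not mention norms, and a percentile of observed trial scores is at least as natural a reading. The sensitivity analyses in SAP 4.2.1 also draw on observed values. SAP 1.1 places coding descriptions in the Analysis Implementation Plan, which is not among the documents, so a definition may exist there. This stands: the +0.67 and +1.17 are conditional on one reading, and defining the reference as the trial's own scores would remove most of the problem.

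The effect is also diluted. One test moves one participant's composite by at most about 0.10 in these examples, against an assumed SD of 0.7. Real decline on other tests can cancel it. With two of 14 tests lost from -3.5, the gain is 2 × 1.174 / 14 = 0.17, and a mean decline of 2 × 1.174 / 12 = 0.20 on the other 12 offsets it. This stands too.

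The plan has partial safeguards. SAP 4.2.1 gives, as an example, imputing the smallest week-48 value observed in the arm, which leaves little room for reversal. SAP 4.1 allows Winsorizing after the data are seen. Neither corrects the primary rule: the first is a sensitivity analysis and is not tied to the participant's own baseline, and the second is optional and not pre-specified.

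A reader might infer that the participants who deteriorate most are the ones scored as improved. The documents do not support that. The reversal affects those with the lowest baselines. Someone who goes from -1.0 to untestable is scored -1.33 even under the norms. Nor do the documents show that people with very low baselines are the most likely to become untestable.

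**Conclusion.** The point holds as a flaw in the direction of scoring. The rule has no link to the participant's own scores, so on a test lost to neurologic disease it records improvement for anyone whose pre-entry z was below the imputed value. That means any baseline below -2.33 if the norms are the reference, and about the lowest 1% of scores on the test if the trial's own scores are.

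The number affected is not given. With 2% to 10% of an arm affected at baseline -3.5 (an assumption) under the normative reading, the arm-mean bias is about 0.05 or less.

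A reader might set the five international motor tests, all lost from -3.5 (5 × 1.174 / 12 = +0.49), beside the 0.5 design difference and conclude that the trial's result is at risk. That compares one participant's score with a difference between arm means. It also needs the normative reading, all five tests at -3.5 and all five lost, with no change on the other seven. The design difference is not threatened unless such missingness is unbalanced between arms. The reason to act is that the rule can give the wrong sign and costs almost nothing to correct.

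**What to change.** Amend SAP 4.1 in two respects.

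1. Define the worst-1% value as the 1st percentile of observed z-scores for that test and battery, pooled over arms and visits, on the z scale with low meaning poor.
2. For a test not done because of neurologic impairment, impute the lower of that value and the participant's own worst observed z on that test at any visit.

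With an observed pre-entry score, the imputed value is then never above baseline, so the change on that test is zero or negative. Declines that the rule already records are kept. Using any visit also covers a pre-entry test that could not be done: the imputed pre-entry value is then no higher than any score obtained later, so regaining the ability to do the test is not scored as decline.

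The cost is one or two SAP sentences and a few lines of code. The sample size does not change. The small downside is that a participant already at the floor who becomes untestable gets zero change on that test, where a decline might be thought more faithful.
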